9.3 Sample Collection Guidelines

Original paraffin-embedded pathology samples will be collected for all enrolled subjects and reviewed centrally for correlative studies. Core size to be obtained from these samples will be at the discretion of the [name].. NOTE: This is not needed prior to enrollment or treatment initiation for eligibility purposes. Prior to or upon enrollment, all specimens are to be sent to the Pathology Department at Northwestern Memorial Hospital at the following address:

[name],, MD
Professor of Pathology
Northwestern Memorial Hospital
[name]
[name]

Tissue samples will be received in the Pathology Department and reviewed centrally. The Pathology Core Facility at Northwestern University will then arrange pick-up of the samples for construction of the TMA.

Phase II Patients Only

Peripheral blood samples will be collected at the time points noted below and banked for future, unspecified use. One red top and one green top tube will be drawn at each time point (see section 5.4), and can be drawn before or after any treatment scheduled for that same day. Samples will be picked up by and stored by the Clinical Trials Pathology Office.

- Baseline (within 28 days prior to start of study treatment) OR day 1 of induction therapy.
- Day 1 of the first 3 maintenance therapy cycles
 - If patient misses/skips any of the first 3 maintenance cycles, every attempt will be made to collect the samples at the next cycle initiation (day 1 of X cycle) for a total of **three** maintenance samples.

9.3.1 Blood Processing & Shipping:

Red Top Tube:

- a. Red top tube should sit upright after the blood is drawn at room temperature for a minimum of 30 minutes to a maximum of 60 minutes to allow the clot to form.
- b. Centrifuge the blood sample at the end of the clotting time for 15 minutes at room temperature at 1500g. If the blood is not centrifuged immediately after the clotting time, the tubes should be refrigerated (4 degrees Celsius) for no longer than 4 hours
- c. Pipette serum into the labeled cryovials, Close caps on the vials tightly.

Note: Be careful not to pick up red blood cells when aliquoting. This can be done by keeping the pipet above the red blood cell layer and leaving a small amount of serum in the tube

- d. Place all aliquots upright in a specimen box or rack in an -80C or colder freezer. All specimens should remain at -80C prior to shipping. The samples should not be thawed prior to shipping.

Green Top Tube:

- a. Transfer/aliquot whole blood from green top tube into **2 cryovials or falcon tubes**. Close caps on the vials tightly.
- b. Place all aliquots upright in a specimen box or rack in an -80C or colder freezer. All

specimens should remain at -80C prior to shipping. The samples should not be thawed prior to shipping.

Samples are to be labeled with the study participant's study ID number. The following parameters must be recorded for each specimen collection:

- Date and time of blood draw
- Time of specimen processing
- Time specimen was frozen

Frozen samples and associated paperwork should be shipped to the Robert H. Lurie Comprehensive Cancer Center Patchcore Facility Clinical Trials Unit (PCF-CTU). Specimens must be shipped via overnight FedEx on dry ice. Email PCF-CTU staff with details of shipment using the email listed below. It is important that samples do not thaw, therefore all packages should be sent Monday-Thursday only; **batch shipping of specimens is allowable**. All packages should be sent to:

Robert H. Lurie Comprehensive Cancer Center of
Northwestern University
Clinical Trial Pathology Office
Attention: NU 12H09
[name]
[name]
[name]
[contact]
[contact]

10.0 STATISTICAL CONSIDERATIONS

10.1 Study Design/Study Endpoints/Data Analysis

10.1.1 Phase I (also refer to section 4.1.2)

The first three patients enrolled on the study will be treated as a single cohort. If none of these first three patients experience a dose-limiting toxicity (DLT; defined below), Phase II of the study will subsequently commence at the same dose.

In the event of one DLT among the first three-patient cohort, an expansion cohort of an additional three patients will be treated at the same dose. Of the second three patients treated, if no additional patients experience DLT, Phase II of the study will commence at the same dose.

In the event of two or three DLT among the first three-patient cohort, or in the event of two or more DLT among the six patients treated in the first and expansion cohorts, dose de-escalation will be studied, with Brentuximab vedotin at 1.2 mg/kg, with the schedule otherwise unchanged, and with Rituximab dose and schedule unchanged. This dose de-escalation will be studied in a cohort of three patients, and if no DLT are observed, the study will commence at this dose schedule.

In the event that one or more DLT are observed at this dose reduction, enrollment will be held and the protocol reviewed.

10.1.2 Phase II

Our null hypothesis is that the combination of rituximab and brentuximab vedotin will yield no difference in the rate of ORR as compared to that observed with historical treatments. The historical ORR for both PTLD and EBV-related

lymphoma of the elderly, when treated with rituximab (with or without chemotherapy is estimated at approximately 50% [1, 2]. Therefore, the optimal two-stage design to test the null hypothesis that $P=0.50$ versus the alternative that $P>=0.70$ (the hypothesized ORR to rituximab plus brentuximab vedotin) has an expected sample size of 24. Under these conditions, if the combination is actually not significantly more efficacious, there is a <0.05 probability (also known as the alpha value) of concluding that it is. If the combination is actually significantly more efficacious, there is a <0.20 probability (also known as the beta value) of concluding that it is not. Early futility may be declared, such that if eight or fewer responses are observed among the first 15 patients enrolled, the trial will be stopped and considered no more efficacious than therapy with rituximab alone.

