NCI	National Cancer Institute
NHL	Non-Hodgkin Lymphoma
ORR	Overall Response Rate
OS	Overall Survival
PBMCs	Peripheral Blood Mononuclear Cells
PD	Progressive Disease
PFS	Progression Free Survival
p.o.	per os/by mouth/orally
PR	Partial Response
PRR	Partial Response Rate
RP2D	Recommended phase II dose
QOD	Every other day
SAE	Serious Adverse Event
SD	Stable Disease
SGOT	Serum Glutamic Oxaloacetic Transaminase
SPGT	Serum Glutamic Pyruvic Transaminase
WBC	White Blood Cells

STUDY SCHEMA

- DLT period (Phase I only): 21 days of induction
- Duration of treatment (Phase I and II): one year, or until POD (whichever occurs first)
- Primary objective assessment: toxicity after week 4 treatment (Phase I only); scans after induction treatment and/or after consolidation treatment (if applicable) (Phase II only)

*This may be repeated once at discretion of treating investigator; see Section 4.0 (TREATMENT PLAN) for details.

DOSING SCHEMA (in weeks, continued for one year total, or until POD)

STUDY SUMMARY

Title	A Phase I-II Trial of Brentuximab Vedotin Plus Rituximab as Frontline Therapy for Patients with Lymphomas of Immunosuppressed States
Version Date	June 14, 2017 (Amendment 8)
Protocol Number	NU 12H09
Phase	I/II
Methodology	Open-label, single-arm
Study Duration	Approximately 30 months
Study Center(s)	Northwestern University, University of Chicago
Objectives	
Primary objectives: Phase I: Evaluate the safety of brentuximab vedotin and rituximab in patients with immunosuppressed lymphoid malignancies and to determine the recommended phase II dose (RP2D) of the combination. Phase II: Evaluate the efficacy of brentuximab vedotin and rituximab in patients with immunosuppressed lymphoid malignancies.
 
Secondary objectives: Phase II:
 
 1. Further evaluate the frequency and severity of toxicity. 2. Further evaluate the efficacy as measured by one-year PFS and OS. 3. Determine the effects of the combination of brentuximab vedotin and rituximab on markers of EBV activation and proliferation. 4. Further evaluate efficacy as measured by time to initiation of cytotoxic chemotherapy. 5. Further evaluate efficacy as measured by observed rates of graft rejection. 
Exploratory objectives (Phase I and II): Correlate response and outcomes with CD30 expression and EBV markers and levels.

Number of Subjects	Phase I: 3-9 patients; Phase II: 24 patients

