10.2 Sample Size and Accrual

For Phase I, we anticipate enrolling either three or six patients, depending on whether one or two cohorts are opened. For Phase II, we plan to enroll 24 patients. This results in a total of 27-33 patients. Under current conditions at our centers, we anticipate being able to successfully accrue patients to this protocol at an average rate of 1.5 per month, resulting in a target time frame of approximately 2-2.5 years for completion of Phases I and II.

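### The Phase II size of 24 is the two-stage design's average size under the null, not its maximum (43), so 24 patients cannot give alpha below 0.05 and beta below 0.20 together

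*Combined protocol and SAP*

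**What the plan says.** Section 10.1.2 (Phase II), repeated under Statistical Methodology in the Study Summary, describes an optimal two-stage design for a null overall response rate (ORR) of 0.50 against an alternative of at least 0.70. It gives the size of that design as an average: "the hypothesized ORR to rituximab plus brentuximab vedotin) has an expected sample size of 24". On the false-positive side it states that "there is a <0.05 probability (also known as the alpha value) of concluding that it is", and on the false-negative side that "there is a <0.20 probability (also known as the beta value) of concluding that it is not". The interim rule is that "if eight or fewer responses are observed among the first 15 patients enrolled, the trial will be stopped".

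The same 24 then appears as the enrolment number. Section 10.2 says "For Phase II, we plan to enroll 24 patients". The Study Summary lists "Phase I: 3-9 patients; Phase II: 24 patients". Section 3.0 caps the whole trial at 33 subjects, which is 9 + 24.

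No section gives a second-stage size, a maximum size for the two-stage design, or the number of responses needed at the end to declare success.

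**The concern.** In a two-stage design with a futility stop, the expected size is an average over trials that stop early and trials that run to the end. It always lies below the maximum. A trial that passes the interim must recruit to the maximum for its alpha and beta to hold. Section 10.1.2 calls 24 an expected size, and the other sections treat it as the total.

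The stated alpha and beta support the primary efficacy conclusion of Phase II. If 24 patients cannot deliver them, a negative result would be read as coming from a trial with 80% power when the power is much lower. Because the final cut-off is missing, it could also be chosen after the responses are known, and the false-positive rate would depend on that choice.

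**Working it through.** **Inputs (all from Section 10.1.2).** p0 = 0.50; p1 = 0.70; alpha below 0.05 (one-sided, as a single-arm test against a higher rate); beta below 0.20; first stage n1 = 15, stopping if responses are r1 = 8 or fewer.

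**Formulas.** Let X1 be the responses in the first n1 patients and X2 the responses in the remaining n − n1. Success requires more than r responses in total.

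- Probability of early stopping: PET(p) = P(X1 ≤ r1 | p)
- Expected size: EN(p) = n1 + [1 − PET(p)] × (n − n1)
- Probability of declaring success: the sum over x = r1 + 1 to n1 of P(X1 = x | p) × P(X2 > r − x | p). This is alpha at p0 and power at p1.

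**Step 1: reproduce the plan's 24.** An exact search over two-stage designs, minimising EN(0.50) subject to alpha ≤ 0.05 and power ≥ 0.80, gives n1 = 15, r1 = 8, n = 43, r = 26. That is: stop at 8 or fewer of 15; otherwise enrol to 43 and declare success with 27 or more responses.

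- PET(0.50) = 22,819/32,768 = 0.696
- EN(0.50) = 15 + (1 − 0.6964) × 28 = 23.5, which rounds up to 24
- PET(0.70) = 0.131, so EN(0.70) = 15 + (1 − 0.1311) × 28 = 39.3
- alpha = 0.0499; power = 0.804

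The first stage is exactly the plan's, and the null expected size is the plan's 24. With the first stage fixed at 8 of 15, 43 is also the smallest total that meets both limits.

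**Step 2: test 24 as the maximum with the same first stage.** The expected size would be 15 + (1 − 0.6964) × 9 = 17.7 under the null and 15 + (1 − 0.1311) × 9 = 22.8 at 70%. Neither is 24, so in Section 10.1.2 the figure fits only the 43-patient design.

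**Step 3: error rates with a maximum of 24 and the 8-of-15 stop.**

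| Success if at least | Alpha (true ORR 50%) | Power (true ORR 70%) | Beta |
|---|---|---|---|
| 15 of 24 | 0.132 | 0.802 | 0.198 |
| 16 of 24 | 0.072 | 0.708 | 0.292 |
| 17 of 24 | 0.032 | 0.561 | 0.439 |

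A cut-off below 15 raises alpha further, and one above 17 lowers power further. No row meets both limits. With 17 of 24, power reaches 80% only at a true ORR of about 76%.

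**Step 4: could another design rescue 24?** Among all two-stage futility designs with a maximum of 24 and alpha ≤ 0.05, the highest power at 70% is 0.618. The smallest total meeting both limits is 37, by either of two designs:

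- Two-stage: stop at 12 or fewer of 23, success at 24 or more of 37 (alpha 0.048, power 0.801).
- Single-stage: success at 24 or more of 37 (alpha 0.049, power 0.807).

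**The case against.** **The sentence in Section 10.1.2 is accurate.** It says expected, and 24 is the expected size. This stands. The error lies in adopting that figure as the enrolment number in the Study Summary and Section 10.2, and in the cap in Section 3.0.

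**The 43-patient design is inferred.** Neither 43 nor 27 appears in the documents. That is so, but the inference is strong, because the stated rates, error limits and first stage lead to that design and reproduce the stated average. The finding that 24 fails does not depend on it, since Step 4 covers every two-stage futility design of that size.

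**Section 7.5 gives a different interim rule, four or fewer responses among 15.** With that rule and a maximum of 24, the null expected size would be 23.5, because PET is only 0.059: 15 + 0.941 × 9 = 23.5. So 24 could be read as both maximum and rounded average under Section 7.5. This does not rescue the claim. At least 17 of 24 would give alpha 0.032 and power 0.565; at least 16 would give 0.076 and 0.725; at least 15 would give 0.154 and 0.847. Again no cut-off meets both limits.

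**43 is not the only size that would support the claim.** Correct: 37 suffices if the 8-of-15 first stage is given up. It is still well above 24.

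**The 24 outcomes may not all be evaluable.** Section 3.1.3 admits patients with fully resected disease, who are not evaluable for objective response, and Section 6.2.1.1 restricts evaluability further. This is a fair point about the fix, which needs a stated denominator. It gives no support to the present claim.

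**Conclusion.** The concern holds. The planned 24 is the average size, under a true ORR of 50%, of a design whose maximum is 43. With 24 patients the stated alpha and beta cannot both be met. At the 17-of-24 cut-off, which keeps alpha below 0.05, the chance of missing a regimen with a true ORR of 70% is about 44%, not below 20%. At the cut-off that brings beta below 0.20 (15 of 24), alpha is 0.132, not below 0.05. Because no final cut-off is stated, the false-positive rate could be anywhere from about 3% to 13% across these three plausible choices.

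The figures assume independent binary responses, response meaning CR or PR, 24 evaluable patients, and the interim rule in Section 10.1.2. Using the Section 7.5 rule changes the 17-of-24 figures only slightly (power 0.565 instead of 0.561). This must be fixed, because the plan's stated error rates for its primary Phase II hypothesis are wrong as written.

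**What to change.** **Recommended: keep 24 as the maximum and state what it delivers.** In the Study Summary, Section 10.1.2 and Section 10.2:

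- Call 24 the maximum and remove the present alpha and beta claim.
- State the full rule: continue if at least 9 of 15 respond; declare success if at least 17 of 24 respond.
- State its properties: one-sided alpha 0.032, power 56% at an ORR of 70%, and 80% at about 76%.
- Alternatively, pre-specify at least 16 of 24, with alpha 0.072 and power 71%.
- State the denominator and what happens if fewer than 24 patients are evaluable.

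Choose the cut-off without reference to observed responses. Section 4.1.1 dates the Phase II dose to March 2014 and this version is dated June 2017, so Phase II patients may already have been treated. Reconcile the interim rules in Sections 10.1.2 and 7.5 at the same time, because the quoted properties assume the former.

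The cost is wording in these sections and a less favourable stated power. No extra patients are needed.

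**If the sponsor wants to keep alpha below 0.05 and beta below 0.20:** with the 8-of-15 first stage, state a maximum of 43 and success at 27 or more. With the Study Summary's 3 to 9 Phase I patients the total becomes 46 to 52, so the cap of 33 in Section 3.0 must change. At the 1.5 patients per month in Section 10.2, accrual takes 46/1.5 to 52/1.5, about 31 to 35 months, against the stated 2 to 2.5 years. A 37-patient design is possible only with a different first stage or none.

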10.2 Sample Size and Accrual

For Phase I, we anticipate enrolling either three or six patients, depending on whether one or two cohorts are opened. For Phase II, we plan to enroll 24 patients. This results in a total of 27-33 patients. Under current conditions at our centers, we anticipate being able to successfully accrue patients to this protocol at an average rate of 1.5 per month, resulting in a target time frame of approximately 2-2.5 years for completion of Phases I and II.

11.0 STUDY MANAGEMENT

11.1 Conflict of Interest

All investigators will follow the Northwestern University conflict of interest policy.

11.2 Institutional Review Board (IRB) Approval and Consent

It is expected that the IRB will have the proper representation and function in accordance with federally mandated regulations. The IRB should approve the consent form and protocol.

In obtaining and documenting informed consent, the investigator should comply with the applicable regulatory requirement(s), and should adhere to Good Clinical Practice (GCP) and to ethical principles that have their origin in the Declaration of Helsinki.

Before recruitment and enrollment onto this study, the patient will be given a full explanation of the study and will be given the opportunity to review the consent form. Each consent form must include all the relevant elements currently required by the FDA Regulations and local or state regulations. Once this essential information has been provided to the patient and the investigator is assured that the patient understands the implications of participating in the study, the patient will be asked to give consent to participate in the study by signing an IRB-approved consent form.

Prior to a patient's participation in the trial, the written informed consent form should be signed and personally dated by the patient and by the person who conducted the informed consent discussion.

11.3 Required Documentation (for multi-site studies)

Before the study can be initiated at any site, the following documentation must be provided to the Clinical Research Office.

- A copy of the official IRB approval letter for the protocol and informed consent
- IRB membership list

- CVs and medical licensure for the principal investigator and any associate investigators who will be involved in the study
- Form FDA 1572 appropriately filled out and signed with appropriate documentation [48]
- A copy of the IRB-approved consent form
- CAP and CLIA Laboratory certification numbers and institution lab normal values
- Executed clinical research contract

11.4 Registration Procedures

Patients *may not* begin protocol treatment prior to registration. All patient registrations will be registered centrally through the Clinical Research Office (CRO) at Northwestern University before enrollment to study. Please contact the assigned QAM or email the CRO's QA Department at [contact] for questions regarding patient registration.

11.4.1 Access to NOTIS

Eligible patients will be registered to the study via the web-based application NOTIS (Northwestern Oncology Trial Information System), which can be found at: <https://notis.nubic.northwestern.edu>. Please note that a username and password is required to use this program, and will be provided during site activation prior to training on the NOTIS system.

11.4.2 Registering a Patient for the Phase I Portion of the Study

For potential patients for the phase I portion of this study, please email the QA department at NU ([contact]) *prior to consenting a patient* to determine whether a slot is available on the current cohort. Slots may be reserved according to the Slot Reservation Procedure (see appendix D). An email confirming the reservation and expiration date will be sent by the QAM. In order for registrations to be processed efficiently, study teams are asked to inform the QAM of the date and time that the patient will need to be registered.

BEFORE a patient can be treated on study, please complete and submit the following items to confirm eligibility and receive a subject identification number:

- Eligibility eCRF (complete in NOTIS)
- Eligibility checklist (signed and dated by the treating physician – upload in NOTIS)
- Signed and dated informed consent document (upload in NOTIS)
- Pathology Report (upload in NOTIS)

Affiliates sites are required to de-identify, scan, and e-mail the following source documents in order to confirm eligibility prior to registration for phase I patients:

- Complete medical and surgical history, current medications, history of clinically significant infections, and physical exam [including weight, height, ECOG PS, vital signs (pulse, temperature, respiratory rate, blood pressure, oxygen saturation)]
- Lab results (ANC, platelets, bilirubin, AST/ALT, creatinine)
- Negative pregnancy test (if applicable)
- Copy of baseline PET/CT report

For Northwestern University (NU) study teams are NOT required to submit a separate email for NU participants, provided that the required documentation listed above is readily available in the patient's electronic medical record (EMR), a separate e-mail submission is NOT required. However, any information that is

not available in the EMR must be de-identified and emailed to the QAM.

The QAM will review all source documentation required to confirm eligibility. Once the QAM confirms the patient is eligible, he or she will register the patient, assign a subject identification number, provide a cohort assignment, and send a confirmation of registration to involved personnel. Registration will then be complete and the patient may begin study treatment.

11.4.3 Registering a Patient to the Phase II Portion of the Study

BEFORE a patient can be treated on study, please complete and submit the following items to confirm eligibility and receive a subject identification number:

- Eligibility eCRF (complete in NOTIS)
- Eligibility checklist (signed and dated by the treating physician – upload in NOTIS)
- Signed and dated informed consent document (upload in NOTIS)
- Pathology Report (upload in NOTIS)

The QAM will review the registration, register the patient, assign an identification number, and send a confirmation of registration to involved personnel.

Registration will then be complete and the patient may begin study treatment.

11.5 Data Management and Monitoring/Auditing

This study will be monitored as a high risk study, which requires high intensity monitoring, as outlined in the [Lurie Cancer Center's DSMP](#). Please refer to NOTIS for more specific details on the monitoring plan and data submission guidelines. All participating sites are responsible for entering data in the timeframe outlined in the data submission guidelines.

